QualDash: Designing and evaluating an interactive dashboard to improve quality of care

Protocol version number and date: 2.0, 11/04/2018

IRAS number: 227139 Funder's number: 16/04/06

Project duration: 33 months (October 1st 2017 to June 30th 2020)

Principal Investigator: [name], School of Healthcare, University of Leeds

Version control

Version	Date	Author	Edits
1.0	03/4/2017		Approved by University of Leeds School of Healthcare Research Ethics
			Committee (ref: HREC16-044)
2.0	11/04/2018		Addition of observation of meetings in Phase 2

Acknowledgement:

This project is funded by the NIHR Health Services & Delivery Research Programme (project number: 16/04/06). The views expressed are those of the authors and not necessarily those of the NHS, the NIHR or the Department of Health.

SUMMARY OF RESEARCH

Background: Quality dashboards provide visualisations of quality data which can lead to the identification of previously unnoticed patterns in that data,¹ informing quality improvement (QI) initiatives, and more efficient and effective decision making.²

Aim: To develop and evaluate QualDash, a web-based quality dashboard for exploring National Clinical Audit (NCA) data. To ensure users can interact with and view audit data in ways that are meaningful to them,³ QualDash will be interactive and tailored to meet the needs of different users. Through the process of individualisation and using novel visualisation techniques, QualDash will support clinical teams, quality sub-committees, NHS Trust boards, and commissioners to better understand and make use of NCA data to improve quality of care and clinical outcomes.

Methods: The project is based on MRC guidance for design and evaluation of complex interventions.⁴ To ensure that QualDash has a robust theoretical basis and to enhance the probability of its widespread implementation, we will combine the principles of realist evaluation (which involves building, testing and refining the theories of how and in what contexts an intervention works)⁵ and principles of co-design.^{6,7} Our project is comprised of five phases:

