Data collection: Interviews will be semi-structured and will follow guidance on the undertaking of realist 'theory gleaning' interviews. To Interviews will start with questions about the participant's role and their experience of, and involvement with, NCAs. To begin to elicit the participant's theories about how and in what contexts NCAs lead to improvements in care quality, we will ask about their perceptions of the impacts of the NCAs, before encouraging them to expand on the contexts in which they perceive those impacts to occur and their ideas about how those impacts are achieved. We will investigate what MINAP and PICANet data are collected (for example, MINAP contains over 130 fields, only 20 of which must be completed) and how, which of these measures are used in making assessments of care quality and informing QI initiatives, what other data participants would like to use for this purpose, and why. In interviews with members of quality sub-committees and Trust boards and commissioners, we will also explore their experience of NCAA, NACR, the Elective Surgery National PROMs Programme, and the BAUS audits. As recommended for co-design, interviews will be conducted at the participants' places of work, providing the opportunity to view and discuss workplace artefacts that participants perceive as relevant. We will discuss the idea of QualDash, to gather participants' perceptions of what QualDash would need to provide, what they perceive the impact of that would be, and the contexts in which they perceive it would provide benefit. The research team will agree revisions to the interview topic guide in light of emerging theories. All interviews will be audio recorded and transcribed verbatim.

Analysis: An iterative approach to data collection and analysis will be taken, to support the refinement of emerging theories. Interview transcripts will be entered into a qualitative software program (NVivo 10) for indexing.

Framework analysis, an approach developed for analysing qualitative data for the purpose of applied research, will be used. Framework analysis is an approach that has previously been used within realist evaluation studies, including our own, and we and have found it to be well suited to working with large data sets. Framework analysis allows for systematic and comprehensive analysis of the collected data and enables both between- and within-case analysis.

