Analysis: The audio recordings will be transcribed verbatim, using the notes to identify speakers, and then annotated with notes of the non-verbal interaction. Analysis of the data will be conducted after each focus group using framework analysis as described above. This analysis will be used to make further refinements to the QualDash program theory and inform the design of the implementation strategy.

Outputs

An implementation strategy and associated resources for QualDash, tailored to each of the five Trusts.

Phase 4: QualDash evaluation Objective

• To understand how and in what contexts QualDash leads to improvements in care quality (Objective 4).

Summary of method

Phase 4 addresses the question 'in what contexts and by what mechanisms do quality dashboards lead to increased engagement with audit data and subsequent improvements in care quality?' (Question D). To evaluate QualDash, we will collect data that will enable testing of the program theory. Realist evaluation does not employ particular methods of data collection, but is explicitly a mixed method approach.⁹⁶ Outcome data, in the form of key MINAP and PICANet process measures, will be collected and analysed in a CITS study, while a multi-site case study⁹⁷ will provide insight into the contexts and mechanisms that lead to those outcomes. CITS studies provide a robust method of assessing the effect of an intervention and have been used to assess the effectiveness of a variety of complex interventions.⁹⁸

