Sample: Data will be collected for sites A-E, with two control Trusts per intervention Trust, matched on comparable outcomes pre-intervention. Contextual factors in the QualDash program theory may be used as additional matching criteria. A CITS study requires data for a minimum of three time points pre-intervention and three time points postintervention and must also allow for any seasonal effect on the outcomes. 106 Therefore, monthly data will be obtained for 24 months pre-intervention and 12 months post-intervention. For MINAP, Cumulative Missed Opportunities for Care (CMOC) will be used as the primary process measure (described below). The average CMOC for patients on a ward will be averaged for each month, so that there are 36 observations clustered within each of 15 hospitals. Taking the intra-class correlation to be 0.15, this yields a design effect of 6.25. Hence the effective number of observations is 15*36/6.25=86.4. Using Cohen's approach to sample size calculation this means that an effect size of 0.17 can be estimated with 80% given that there are six parameters in the model (including the coefficient for QualDash). Converting this to the percentage of variation that can be explained by the model, this yields 20.5%. Translating this back to CMOC, currently 49.6% are discharged from hospital without missing any of the nine opportunities for care, and we would be powered at the 80% level to detect an improvement from an average of 8.33 opportunities achieved to 8.46. Thus our study has good power to detect small but meaningful clinical improvements. For PICANet, the primary process measure will be the use of non-invasive ventilation first for patients requiring ventilation, 10% of the admitted population. 107 On average there are 5.25 ventilation cases per month per hospital. With a further design effect from patients clustered within hospitals, based on the reported ICC=0.065 giving DEff=1.276, the actual anticipated number of patients is 1701 giving an effective number of 213: 71 exposed to QualDash and 142 controls. This yields 80% power to detect a change from 32% to 53% which is a feasible target given that the use of non-invasive ventilation first will be highlighted by QualDash.

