Data collection: For MINAP, the primary outcome will be the composite process measure CMOC. This has nine components (pre-hospital ECG, acute use of aspirin, timely perfusion, prescription at hospital discharge of aspirin, thienopyridine inhibitor, ACE-inhibitor, HMG-CoA reductase inhibitor, beta blocker, referral for cardiac rehabilitation) and, in previous work by members of the team, CMOC has been shown to be associated with mortality. ¹⁰⁸ For PICANet, the primary outcome will be use of non-invasive ventilation first for patients requiring ventilation, which has been shown to be associated with reduced mortality. ¹⁰⁷ Secondary outcomes will be determined on the basis of findings from Phase 1 regarding interviewees' perceptions of the value of particular measures and the extent to which they can be impacted by QI initiatives and through consultation with our LAG.

Analysis: Monthly MINAP and PICANet data will be extracted to spreadsheets for analysis with R software. ¹⁰⁹ For each intervention Trust, there will be 72 data points prior to introduction (24 for the intervention Trust and 48 for the control Trusts) and 36 data points post intervention (12 for the intervention Trust and 24 for the control Trusts). For both NCAs, the outcome will be regressed upon time and the intervention (QualDash). The time component will include a seasonal effect (quarterly effect) and will allow for a (linear) time trend. To account for clustering of monthly observations within hospitals a random intercept will be fitted, although a fixed effect for hospital as a sensitivity analysis will be explored. Although the intervention is abrupt, its impact may well be 'phased in' over a few months, perhaps three. The timing of the bedding in of the intervention will be reported from the multi-site case study. Then a partial effect can be considered for this period with the interaction effect stepping up in a linear fashion.

4b. Multi-site case study

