The commissioning brief emphasises the need for trials within NCAs to test the principles of effective communication of NCA data to key audiences. We will use the findings of Phase 4 to determine for whom and in what contexts a trial of QualDash is appropriate. This avoids the cost of a trial if QualDash is found to be ineffective while, if the results of Phase 4 suggest QualDash does provide benefit, we will be able to design a trial that is fit for purpose, with high internal and external validity, for which subsequent funding would be sought.^{113,114}

Progression criteria will be: (i) QualDash is used by 50% or more of the intended users; (ii) data completeness in the NCA improves or remains the same; and (iii) participants perceive QualDash to be useful and express the intention to continue using it after the study period. Criteria (i) and (iii) are concerned with acceptability and uptake of the intervention, and therefore have implications for recruitment to a trial. The second criterion is concerned with ensuring that the intervention does not have unintended negative consequences which would affect both the success of the intervention (as QualDash will be less useful if data completeness is reduced) and the feasibility of outcome assessment. The third criterion is also concerned with participants' perceptions of the impact of QualDash on care. While not formally assessed as part of the progression criteria, the impact of QualDash on processes of care as identified in the CITS will also be considered in determining whether a future CRT is justified. A traffic light system will be used to determine if a trial is feasible (green), feasible with modifications to QualDash and/or the implementation strategy (amber), or not feasible (red). 113,115

If a trial is found to be feasible, a CRT will be designed. It is anticipated that the primary outcome will be a patient outcome. Data from the CITS will be used to inform the selection of NCAs to be included in the trial (MINAP and/or PICANet) and will provide information about variability of outcomes and about how long a trial intervention period would need to be. Findings from the multi-site case study will be used to inform the selection of categories of user to be included in the trial and, associated with this, the level of randomisation (Trust, hospital, or ward).

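### The controlled interrupted time series has no check on recording, so a QualDash-induced rise in MINAP recording could produce some or all of the targeted CMOC gain

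*Protocol*

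**What the plan says.** The Summary of Research describes the intervention as "QualDash, a web-based quality dashboard for exploring National Clinical Audit (NCA) data". The Phase 4 summary of method says: "Outcome data, in the form of key MINAP and PICANet process measures, will be collected and analysed in a CITS study".

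Section 4a fixes the outcomes. "For MINAP, the primary outcome will be the composite process measure CMOC", built from nine components. For PICANet the primary outcome is use of non-invasive ventilation first. On the data source: "Monthly MINAP and PICANet data will be extracted to spreadsheets for analysis with R software". The model regresses the outcome on time (a quarterly seasonal effect and a linear trend) and the intervention, with a random intercept for hospital. There are two control Trusts per intervention Trust, matched on pre-intervention outcomes, and contextual factors from the program theory may be added to the matching.

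The Sample paragraph claims 80% power to "detect an improvement from an average of 8.33 opportunities achieved to 8.46". For PICANet it calls a move from 32% to 53% feasible, "given that the use of non-invasive ventilation first will be highlighted by QualDash".

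Completeness is mentioned in three other places:
- Setting/context says that the two audits differ in data quality and completeness.
- Section 1a notes that "MINAP contains over 130 fields, only 20 of which must be completed".
- In Phase 5, progression criterion (ii) is met if completeness rises or holds steady. The reason given is that a fall would harm both the intervention, "as QualDash will be less useful if data completeness is reduced) and the feasibility of outcome assessment".

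**The concern.** The time series is meant to show impact on processes of care. Its outcomes are counts of what was recorded in the audits, and the intervention feeds data from those audits back to Trusts. Care that was given but not entered, and is entered once a Trust starts looking at its figures, raises the measured outcome without changing care.

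Control Trusts remove a recording trend common to all Trusts. They cannot remove one that starts when QualDash is introduced and occurs only where it is introduced. In the stated model that change falls on the QualDash coefficient.

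The Protocol recognises that completeness may move and that this bears on outcome assessment, but it guards only against a fall. A rise, which is the direction that could inflate CMOC, counts as a pass. The CITS result is also to be considered in deciding whether a randomised trial is justified, and is to inform the effect size that trial is powered for. A recording effect read as a care effect would carry into that planning.

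**Working it through.** **Inputs** (section 4a, Sample, unless stated): 36 monthly observations in each of 15 hospitals; intra-class correlation 0.15; effect size 0.17; six parameters; 49.6% of patients with no missed opportunity; mean CMOC 8.33 rising to 8.46 of nine; PICANet 32% rising to 53%. The Protocol gives no completeness figure.

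**1. The plan's own MINAP figure.**
- Design effect: 1 + 35 × 0.15 = 6.25. Effective observations: 15 × 36 / 6.25 = 86.4. Both match.
- Power, taking 0.17 as Cohen's f² with six numerator degrees of freedom, N = 86.4 and α = 0.05 (assumed, as none is stated): 79.9%, against the stated 80%.
- One route to the CMOC values is nine equal, independent components. Then p = 0.496^(1/9) = 0.925, mean 9 × 0.925 = 8.325, SD 0.790, and 8.325 + 0.17 × 0.790 = 8.460. This reproduces 8.33 and 8.46. The steps below use only those two values.

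**2. Size of the targeted gain.**
- 8.46 − 8.33 = 0.13 opportunities per patient.
- Per component: 0.13 / 9 = 1.44 percentage points if every newly recorded item was delivered, or 0.13 / 8.33 = 1.56 points if newly recorded items are positive at the baseline rate of 8.33/9.
- As a share of counted misses: 9 − 8.33 = 0.67, and 0.13 / 0.67 = 19.4%. Allowing for rounding of both means, the range is 18.0% to 20.7%.

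**3. When recording alone reaches 8.46.** Assume blanks count as missed. Let r be the share of counted misses that were given but not recorded, and q the share of those newly recorded in intervention Trusts. The measured mean becomes 8.33 + 0.67 × r × q, so the whole gain needs r × q ≥ 0.194. The values of r and q below are assumed:

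| r | q = 50% | q = 100% |
|---|---|---|
| 10% | 8.36 | 8.40 |
| 20% | 8.40 | 8.46 |
| 30% | 8.43 | 8.53 |
| 40% | 8.46 | 8.60 |
| 50% | 8.50 | 8.67 |

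Put as the share of delivered care that is recorded, the required new level is the old level × 8.46 / 8.33. From 95.0% this gives 96.5%, and from 98.0% it gives 99.5%: a rise of about 1.5 points in each case.

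**4. Upper limit under the same assumption.** If blanks count as missed, average completeness of the nine items is already at least 8.33 / 9 = 92.6%, so there is limited room for recording to improve.

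**5. PICANet.** The target is 53 − 32 = 21 points, out of 100 − 32 = 68 points not recorded as non-invasive first. Recording alone would have to reclassify 21 / 68 = 31% of those cases.

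**6. If blanks are dropped instead.** Newly recorded patients or items change the set being averaged. The Protocol gives nothing from which to derive the direction of that effect.

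**The case against.** The strongest objection is that blank handling and sensitivity analyses normally belong in a statistical analysis plan, which is not shown. This stands in part: the missing blank rule is not itself the fault. But the Protocol itself fixes the audit extract as the outcome source, sets out the model, and gives completeness its only role as a one-sided progression criterion.

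A second objection is that Phase 4 uses mixed methods. Section 1a asks what audit data are collected and how, section 4b plans at least 384 hours of observation, and the narrative analysis brings in the CITS results. That work could well reveal a change in recording practice. However, nothing ties what it finds to the CITS estimate.

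A third is that the 1.44-point figure makes the shift look easy. The same gain needs about a fifth of all counted misses to be delivered, unrecorded, and then newly recorded in intervention Trusts only. That is right, and both figures should be read together.

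A reader might infer something stronger: that both primary outcomes are compromised, that a positive result would be an artefact, and that Objective 4 would go unanswered. The documents do not support this.
- The statement about compulsory MINAP fields does not show that any of the nine CMOC fields is optional.
- Only non-invasive ventilation is said to be highlighted by QualDash. Nothing says that CMOC will be displayed.
- Section 1a describes audit data as produced by some staff and used by others, so those who record need not be those who view.
- Reclassifying 31% of PICANet cases by recording alone is much less plausible than the CMOC shift.
- Objective 4 is addressed by the CITS and the case study together.

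**Conclusion.** The point holds as a weakness in interpretation, mainly for CMOC. The outcome source and the content of the dashboard come from the same audits. The controls and the stated model cannot separate a QualDash-induced change in recording from a change in care, and the only completeness rule treats a rise as success.

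If unrecorded items count as missed, a recording rise of 1.44 to 1.56 points per component, confined to intervention Trusts, would equal the whole targeted gain of 0.13. Equivalently, 19.4% of the 0.67 counted misses would have to be recovered by recording; smaller recoveries give part of the gain.

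This says what could happen, not what will. It rests on an unstated rule for blanks, on no known completeness level, and on the nine fields not already being fully recorded. If blanks are dropped, the direction is unknown. The whole-gain statement applies to CMOC only.

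**What to change.** In section 4a, Analysis, add three items:

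1. Run the same controlled time series on monthly completeness of the nine CMOC fields and of the PICANet ventilation fields, in intervention and control Trusts.
2. Report CMOC twice: with unrecorded items counted as missed, and using recorded opportunities only.
3. Report the completeness effect beside the CITS estimate. Where completeness rises in intervention Trusts, or the two versions of CMOC disagree, state that the effect may reflect recording as well as care, and draw on what the case study found about recording practice.

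Item 3 is a reporting requirement, not a pass/fail rule. A rule requiring both versions to agree would have no natural threshold, and could block a sound conclusion if QualDash improved both recording and care.

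The outcomes, sites and data source stay as they are, and completeness already has to be assessed for progression criterion (ii). The cost is a little more analysis and a more cautiously worded positive result.

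### The controlled interrupted time series model, as described, names no post-launch term shared with the controls and no group-specific trend, so part of a common change at launch, or a pre-existing slope gap, would be credited to QualDash

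*Protocol*

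**What the plan says.** All references are to the Protocol, Phase 4, section 4a.

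- **Model (Analysis).** For both audits "the outcome will be regressed upon time and the intervention (QualDash"). On time: "The time component will include a seasonal effect (quarterly effect) and will allow for a (linear) time trend".
- **Hospitals (Analysis).** "a random intercept will be fitted, although a fixed effect for hospital as a sensitivity analysis will be explored".
- **Phase-in (Analysis).** After suggesting that the impact may build up over about three months: "Then a partial effect can be considered for this period with the interaction effect stepping up in a linear fashion". This is the only mention of an interaction. Its components are not given.
- **Power (Sample).** For MINAP, "an effect size of 0.17 can be estimated with 80% given that there are six parameters in the model (including the coefficient for QualDash"). The six are not listed.
- **Controls (Sample).** "two control Trusts per intervention Trust, matched on comparable outcomes pre-intervention". Contextual factors from the program theory may be added as matching criteria. Pre-launch trend is not mentioned.
- **Length (Sample).** "monthly data will be obtained for 24 months pre-intervention and 12 months post-intervention".

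**The concern.** Control Trusts protect the estimate only if the model lets all Trusts depart from a straight line together. With one shared trend and quarterly effects, a change that reaches every Trust at launch (for example in national practice or recording) has no term of its own. It is split between the trend, the residuals and QualDash.

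A second gap concerns slopes. If intervention Trusts were already improving faster or slower than their controls, a shared trend cannot show it, and the difference builds up in the QualDash term. A random or fixed hospital intercept removes differences in level, not in slope.

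The estimate matters beyond this study. The research summary says that the time series results will set the effect size for a future cluster trial, and Phase 5 says that they will be considered when deciding whether that trial is justified.

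**Working it through.** **Inputs (section 4a).** 5 intervention and 10 control hospitals for MINAP (3 and 6 for PICANet); 24 months before and 12 after launch; ICC 0.15; MINAP target 8.33 to 8.46, a difference of 0.13; PICANet target 32% to 53%, or 21 points. Assumed: two-sided alpha 0.05, quarters aligned with month 1, QualDash = intervention Trust × post-launch.

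**1. The plan's own figure.** Design effect 1 + 35 × 0.15 = 6.25; effective N = 15 × 36 / 6.25 = 86.4. Cohen's f² at 80% power comes from the noncentral F distribution, with u predictors, v = 86.4 − u − 1 and noncentrality f²(u + v + 1):

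| Predictors besides the intercept | v | f² at 80% power | Power at f² = 0.17 |
|---|---|---|---|
| 5 | 80.4 | 0.159 | 0.830 |
| 6 | 79.4 | 0.1705 | 0.799 |

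The stated 0.17 is reproduced with six predictors besides the intercept. The terms named in the text give five: trend 1, quarters 3, QualDash 1. There is room for one more. A post-launch term and a group slope together would need seven.

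**2. Bias under the model as written, hospital fixed effects.** The bias is the coefficient obtained by regressing the omitted pattern on the model's terms. The treated share is 1/3, so the between-group factor is 1/3 × 2/3 = 2/9.

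- Within a hospital, the post-launch indicator has sum of squares 36 × (1/3)(2/3) = 8. After removing trend and quarters, 2.041 is left.
- Sum of squares of the QualDash term given the other terms: 15 × (2/9) × 8 + 15 × (1/9) × 2.041 = 26.67 + 3.40 = 30.07.
- *Step of 1 in all Trusts at launch:* 15 × (1/3) × 2.041 = 10.21; 10.21 / 30.07 = **0.34**.
- *Extra slope of 1 per month in intervention Trusts:* the cross-product of month with the post-launch indicator is 12 × (30.5 − 18.5) = 144; 15 × (2/9) × 144 = 480; 480 / 30.07 = **16.0**.

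The same projection by generalised least squares, with a random intercept at ICC 0.15, gives **0.32** and **18.0**. Results are identical for 9 hospitals. Fitting a three-month linear phase-in hardly changes them (0.32-0.34 for an abrupt common step, about 17d-19d for the slope gap).

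**3. What would mimic the whole target effect.**

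| | MINAP (0.13) | PICANet (21 points) |
|---|---|---|
| Common step | 0.13/0.34 to 0.13/0.32 = 0.38-0.41 | 62-66 points |
| Slope gap per month | 0.13/18.0 to 0.13/16.0 = 0.007-0.008 | 1.2-1.3 points |

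The PICANet figures treat the proportion on a linear scale.

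**4. After the change.**

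- *Common post-launch term or calendar-month effects:* the QualDash sum of squares becomes 26.67. Common-step bias is 0. Slope bias is 480 / 26.67 = 18d with hospital fixed effects, and about 20d with a random intercept and no group main effect. Standard error ratio √(30.07/26.67) = 1.06.
- *Group-by-linear-time added as well:* the sum of squares of month is 36 × (36² − 1)/12 = 3885; 8 − 144²/3885 = 2.66; 15 × (2/9) × 2.66 = 8.88. Both biases are 0 with hospital fixed effects. Standard error ratio √(26.67/8.88) = 1.73 on top, or √(30.07/8.88) = 1.84 over the written model.

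**The case against.** The strongest reply is that the model is not fully listed. The six parameters are unnamed, the stated 0.17 fits six predictors better than five, and calling QualDash an interaction suggests a group-by-period contrast with its period main effect. With that term included, the common-step bias is zero. The full term list may sit in a statistical analysis plan that is not shown, and the steering committee, which is to include an expert in this design, reviews the Phase 4 evaluation before it starts.

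Much of this stands. A reader might infer that the parameter count proves the period term is missing; it does not. What remains is that the Analysis paragraph names its terms without a shared post-launch term, and the interaction is mentioned only in an optional phase-in remark. Six predictors also cannot hold both a post-launch term and a group slope, so the slope bias survives either reading.

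Two further objections limit the size. To mimic the 0.13 target, a common step must be 0.38-0.41 opportunities. The possible gain is only 9 − 8.33 = 0.67, so that is roughly 60% of it, in every Trust at once; smaller steps bias in proportion. Further matching criteria are also allowed, and comparable prior outcomes need not mean level alone, so the Protocol does not rule out matching on trend. It only fails to name it.

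**Conclusion.** The point holds for the model as worded. It credits QualDash with 32-34% of any step common to all Trusts at launch and with about 16-18 months' worth of any pre-existing slope gap. The common-step part falls away if an unlisted sixth predictor is a post-launch term. The slope part does not.

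Three stronger conclusions are tempting but unsupported. A common change is not credited in full; the trend and the controls absorb about two thirds. Nor do the documents show that a slope gap exists: Table 1 shows that the sites differ in level, but no between-Trust trend is reported, so 0.007-0.008 per month is a conditional sensitivity. And the estimate does not formally decide whether a trial goes ahead: Phase 5 keeps it outside the progression criteria, although it is considered alongside them and informs the future effect size.

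The figures assume 1:2 allocation, 24 + 12 months, quarters aligned with launch and, for the random-intercept values, ICC 0.15. A launch within a quarter raises the common-step share to 0.37-0.39.

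**What to change.** 1. **Primary model.** Include a post-launch main effect for all Trusts, or calendar-month effects common to all hospitals. Define QualDash as the intervention-group-by-post-launch interaction, and state which terms the phase-in applies to. This removes the common-step bias for about a 6% larger standard error.
2. **Sensitivity model.** Step 1 leaves the slope bias in place (18d-20d), so pre-specify one model that adds intervention group by linear time. Its standard error is about 70% larger again, which is why it suits a sensitivity rather than the primary analysis.
3. **Matching.** Consider pre-launch trend as well as level when choosing controls; the 24 pre-launch months make this possible.
4. **Power.** List the parameters and restate the count and detectable effect for the model actually fitted.

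Items 1, 2 and 4 change wording only, and item 3 uses data already planned. The real cost is the precision given in items 1 and 2.

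### The CITS model allows only for a constant hospital level, so serial correlation or unequal change between hospitals would make the QualDash standard error too small, and the planned sensitivity analysis would not show it

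*Protocol*

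**What the plan says.** The Protocol, Phase 4, 4a, Analysis, regresses each primary outcome on time (linear trend and quarterly season) and on QualDash. It then fixes the dependence structure: "To account for clustering of monthly observations within hospitals a random intercept will be fitted". The only check on that structure that the section names is the alternative of fixed hospital terms: "although a fixed effect for hospital as a sensitivity analysis will be explored". No other device for within-hospital dependence is named: no autocorrelation, no hospital-specific slope or post-period change, and no robust or hospital-level inference.

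Under Sample, "monthly data will be obtained for 24 months pre-intervention and 12 months post-intervention", with "two control Trusts per intervention Trust, matched on comparable outcomes pre-intervention". For MINAP the months are averaged "so that there are 36 observations clustered within each of 15 hospitals". The sample size uses the same idea, a single correlation shared by all pairs of months: "Taking the intra-class correlation to be 0.15, this yields a design effect of 6.25".

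**The concern.** A random intercept makes any two months in a hospital equally correlated, whether adjacent or three years apart, and lets hospitals differ only by a fixed offset. QualDash is almost entirely a within-hospital before-after contrast, so that offset drops out and the remaining months are treated as independent replicates. Two features break this: residual correlation that fades with time, and hospitals whose level shifts by different amounts after the start date.

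The protocol itself makes the second plausible among intervention sites. Phase 3 tailors implementation to each Trust. Phase 2 involves only one Trust in design, so that dependence of success on that involvement can be assessed. Only five treated hospitals carry the MINAP contrast and three (sites A–C) the PICANet contrast.

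The result is used. The Summary says it will set the effect size for a later cluster trial, and Phase 5 says CITS impact will be considered in judging whether that trial is justified.

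**Working it through.** **Plan's own figures.** Design effect 1 + (36 − 1) × 0.15 = 6.25, and 15 × 36 / 6.25 = 86.4: "Hence the effective number of observations is 15*36/6.25=86.4" reproduces. With six parameters and 5% assumed, 80% power needs Cohen's f² = 0.1705, matching the stated 0.17. The arithmetic is sound, given one exchangeable correlation.

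**Inputs from the protocol.** 24 + 12 months; 15 hospitals, 5 treated; ICC 0.15; the stated mean model. **Assumed, not in the documents:** lag-1 residual correlation ρ (AR(1)), SD of hospital-specific post-period change (applied to all hospitals), 5% two-sided level, common start date.

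**By hand, one hospital.** In units of residual variance, the variance of post mean minus pre mean is V = v(24) + v(12) − 2c. Here v(n) = (1/n)[1 + 2Σ(1 − k/n)ρᵏ], summed over k = 1 to n − 1, and c is the covariance of the two means.
- ρ = 0: V = 1/24 + 1/12 = 0.125, which is what an intercept-only model assumes.
- ρ = 0.2: V = 0.0614 + 0.1207 − 2 × 0.0011 = 0.1799. SE ratio √(0.1799/0.125) = 1.20; rejection 2[1 − Φ(1.96/1.20)] ≈ 10%.
- ρ = 0, change SD 0.25: V = 0.125 + 0.0625 = 0.1875. Ratio 1.22; rejection ≈ 11%.

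**Full stated model.** The random-intercept SE comes from (X′V⁻¹X)⁻¹ at ICC 0.15; the true SE is that of the same estimator under the assumed correlation. SEs are in units of the total SD of a hospital-month.

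| ρ | change SD | model SE | true SE | rejection, random intercept | rejection, fixed effect |
|---|---|---|---|---|---|
| 0 | 0 | 0.163 | 0.163 | 5.0% | 5.0% |
| 0.1 | 0 | 0.163 | 0.178 | 7.2% | 7.4% |
| 0.2 | 0 | 0.163 | 0.194 | 9.9% | 10.5% |
| 0.3 | 0 | 0.163 | 0.212 | 13.2% | 14.2% |
| 0.4 | 0 | 0.163 | 0.234 | 17.1% | 18.6% |
| 0 | 0.25 | 0.163 | 0.199 | 10.8% | 10.2% |
| 0.2 | 0.25 | 0.163 | 0.225 | 15.5% | 15.5% |

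The fixed-effect column re-estimates the residual variance and tracks the random-intercept column. Simulated REML fits agree (ρ = 0.3: 13.5% random, 13.1% fixed). Adding a common post-period term changes little.

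**PICANet.** 1701 / (5.25 × 36) = 9 hospitals, and 1701 / 1.276 / 6.25 = 213, so both design effects are applied. At 32%, patient variance is 0.32 × 0.68 = 0.2176.
- All hospital-plus-month variance: 0.065 × 0.2176 = 0.0141.
- Binomial noise in a monthly proportion: 0.935 × 0.2176 / 5.25 = 0.0388. Total 0.0529.
- Constant hospital part: 0.15 × 0.0529 = 0.0079, leaving 0.0141 − 0.0079 = 0.0062 that could be serially correlated.
- Ceiling on residual lag-1 correlation: 0.0062 / (0.85 × 0.0529) ≈ 0.14.

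With all of the 0.0062 treated as AR(1), rejection is about 6% at latent persistence 0.2, 9% at 0.6 and 14% at 0.9.

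**Alternative test.** A t-test on each hospital's post-minus-pre change (H − 2 df) rejected 4.8–5.3% in every simulated scenario, with 15 and with 9 hospitals.

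**The case against.** The strongest objection is that the protocol gives no autocorrelation, no between-hospital variance of change and no significance level, so no inflated error rate follows from it. That stands as to size. A reader might infer that the test rejects 11–28% of the time. The documents do not support this: the rate is 5% without dependence and about 7% at ρ = 0.1. Reaching 28% takes, for instance, ρ = 0.2 with a change SD of 0.5 residual SD, which exceeds the between-hospital SD implied by ICC 0.15 (√(0.15/0.85) = 0.42). Nor do MINAP-sized rates carry over to PICANet, where 19% or 27% is hard to square with the stated case numbers.

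A second objection is that residual covariance and degrees of freedom belong in a SAP. That stands only in part. The protocol names the random intercept, names the sensitivity analysis and sizes the study on the same structure, so this is a stated choice. It does not, however, rule out further modelling. Project Management also plans a CITS expert on the steering committee and a review of the evaluation design at the end of Phase 3, which is a natural point to amend it.

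A third temptation is to conclude that a false positive would by itself trigger a trial. Phase 5 says otherwise: CITS impact is considered but is not a formal progression criterion. The fault also lies in the standard error; no bias in the effect estimate has been shown.

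**Conclusion.** The point holds conditionally. As stated, the main and sensitivity analyses both assume that nothing but a constant level links a hospital's months. Any positive residual serial correlation, or any hospital-specific change, makes the QualDash standard error too small, and agreement between the two fits would give false reassurance.

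For MINAP, a nominal 5% test runs from 5% to about 17% as ρ goes from 0 to 0.4, and reaches about 11–16% with a change SD of 0.25 residual SD and ρ of 0 to 0.2. For PICANet roughly 6–14% is likely, because binomial noise from 5.25 cases a month dominates. That range rests on the protocol's ICCs and treats all remaining month-level variance as serially correlated. Tailored implementation supports unequal effects among treated hospitals; unequal drift among controls is an assumption.

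**What to change.** Amend the 4a Analysis text before Phase 4 data are analysed, in one of two ways.

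1. Keep the stated mean model, add an AR(1) or similar within-hospital residual and a random hospital-level post-period change, and use small-sample degrees of freedom (Kenward-Roger or Satterthwaite). The operating characteristics of this version have not been simulated here and should be checked.
2. Compare each hospital's post-minus-pre change between intervention and control hospitals with a t-test on H − 2 df (13 for MINAP, 7 for PICANet). This is the simpler form, and its error rate was checked. It needs the pooled hospitals; one Trust with two controls leaves a single degree of freedom.

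Keep the random-intercept fit as secondary. A permutation test within matched sets can only be supportive for PICANet: 3³ = 27 assignments, so the smallest possible p is 1/27 = 0.037.

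No new data are needed, and standard R code suffices. The cost is wider intervals. Even with no dependence, option 2 for MINAP has SE √[0.85 × 0.125 × (1/5 + 1/10)] = 0.179 and half-width 2.16 × 0.179 = 0.386, against 1.96 × 0.163 = 0.319, about 21% wider. The stated power should be revisited accordingly.
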